### 1. Abstract

Kabuki syndrome is a rare genetic disorder characterized by intellectual disability and a unique cognitive profile. Studies in a mouse model of Kabuki syndrome have demonstrated hippocampal memory defects and a disruption of adult neurogenesis in the the dentate gyrus. Interestingly, these deficits were normalized in postnatal life with agents that inhibit histone deacetylases, indicating that Kabuki syndrome may be a treatable cause of intellectual disability. Preliminary data shows that patients with Kabuki syndrome have deficits in visuospatial reasoning and memory. This proposal aims to build upon the basic science and clinical work to evaluate a potential treatment using disease-specific outcome measures. If successful, these studies will yield insights into the pathogenesis of Kabuki syndrome and lead to the first therapeutic strategy.

### 2. Objectives

Objective 1: Test whether HDAC inhibition through modified Atkins diet modifies the neurocognitive or neurobehavioral phenotype in individuals with Kabuki syndrome. Previously, a ketogenic diet has been shown to ameliorate cognitive and neurohistological defects in a mouse model of Kabuki syndrome. This proposal aims to conduct a pilot study of 10-15 adult patients with Kabuki syndrome given 12 weeks of HDAC inhibition through diet and determine whether performance on the cognitive assessment protocol changes.

### 3. Background

Kabuki syndrome (KS; MIM 147920) is a genetic disorder occurring in about 1 in every 32,000 births characterized by five cardinal features; dysmorphic facial features, skeletal anomalies, persistence of fetal fingertip pads, postnatal growth deficiency, and intellectual disability (ID). The most common variants in patients with KS are found in KMT2D – a histone methyltransferase that adds mono-, di- and trimethylation to K4, changes found at enhancers and actively transcribed promoters. Mutations in KDM6A – a histone demethylase that removes H3K27me3, a modification seen in closed chromatin - represent another known, but less common cause of KS (MIM 300867). Mutations in KMT2D or KDM6A thus result in widespread changes in normal cellular transcription due to loss of histone modifications resulting in too much closed chromatin. Kabuki syndrome is thus an excellent example of a Mendelian disorder of histone machinery (MDEM), most of which, like KS, result in intellectual disability. In addition to information about a specific rare disease, understanding more about the cellular mechanisms resulting in impaired cognition in KS gives insight into the whole group of MDEMs. Understanding these as a group, in turn, may provide a window into the mechanisms underlying normal cognition and memory and learning, and pathologic states – specifically intellectual disability.

Intellectual disability (ID) is a heavy burden on patients, family and society. Many genetic syndromes result in intellectual disability; however, although the causative genes of these syndromes are known, little is understood about how these variants lead to intellectual disability. Only recently, basic science has begun to try to characterize the mechanisms underlying cognitive impairment. This work has led to treatment trials in diseases such as Fragile X syndrome and Angelman syndrome. The [name] lab has demonstrated that Kmt2d is highly expressed in the granule cell layer of the dentate

gyrus. Kmt2d +/ $\beta$ Geo mice have many physical features of humans with KS as well as abnormalities in visuospatial memory and deficits in neurogenesis in the dentate gyrus region of the hippocampus seen in association with a thinner granule cell layer. Importantly, these cognitive and histopathologic deficits were corrected with postnatal administration of a histone deacetylase inhibitor and with the ketogenic diet. The dentate gyrus – and postnatal neurogenesis in this region – has been linked to spatial pattern separation and thus tests that examine visuospatial reasoning and memory at least partially localize to this brain region. While problems with visuospatial areas of cognition are far from a 1:1 correlation with dentate gyrus neurogenesis, there is certainly an important correlation. Thus, we would expect this neuroanatomical region to be abnormal in individuals with KS if mouse studies are predictive. Our recently published study of 23 patients solidified the visuospatial/verbal differences in the KS cognitive profile and more specifically linked the weaknesses in the profile to the dentate gyrus region. Additionally, by comparing the KS patients to age and IO-matched controls, we established that this cognitive phenotype is specific to Kabuki syndrome and different from what is seen in other causes of ID. In addition, impaired neurogenesis in the hippocampus has been strongly linked to anxiety and anecdotally we have noticed a significant burden of anxiety in patients with Kabuki syndrome. Thus it is important to examine emotion and behavior in totality as well as anxiety in depth in this population and determine whether anxiety moderates the cognitive performance. As a next step, a biologically relevant and evidence-based treatment must be selected as an intervention for a clinical trial.

The [name] lab has demonstrated that in the Kmt2d  $+/\beta$ Geo mice, a ketogenic diet is equally effective in reversing the visuospatial deficits and increasing neurogenesis in the dentate gyrus. This is a treatment that is used clinically for many conditions including ones that affect the central nervous system like epilepsy. Modified Atkins diet has been shown to be effective in these conditions in place of stricter ketogenic diet and is easier for patients to tolerate. The pilot treatment trial we propose here could lead to a larger trial which could have immediate benefit to patients and change clinical practice. The [name] lab demonstrated in 2016 that neurogenesis and memory deficits in the mouse model of KS was not only rescued by administration of HDAC inhibitor AR-42, but that it was also rescued with the ketogenic diet (Figure 2). Beta hydroxybutyrate, a ketone body that is actively transported into the central nervous system and enters the hippocampus during ketosis, is a potent HDAC inhibitor. Modified Atkins diet (MAD) has been shown to be an effective, safer to initiate, and easier to comply with substitute for the ketogenic diet in other CNS processes like epilepsy. Thus we believe the rationale is there to attempt a low-risk pilot study using this intervention in patients with KS. The Neurology teams at Johns Hopkins include nutritionists, clinicians, and researchers who have extensive experience with MAD and they will be available for consultation and for any diet-related needs. 12 weeks was chosen because that is the minimum amount of time used to see effect in studies on the ketogenic diet or MAD. Additionally, 8 weeks is the approximate length of time of neurogenesis of a new neuron. Since we suspect neurogenesis plays a role in cognitive performance in KS, the 12 week duration allows for neurogenesis to take place. To date, no study of treating epilepsy in KS with ketogenic diet or MAD exists.

 Date of last protocol revision:
 3/7/2022\_\_\_\_\_

 Principal Investigator:
 [name]\_\_\_\_\_

 JHM IRB Application Number:
 IRB00250195

# 4. Study Procedures

a. Participants with Kabuki syndrome 18 years and older will be recruited to participate. Recruitment will stop once fifteen participants are consented. This number allows for the ~30% rate of dropout expected based on difficulty complying with the diet in order to have data from 10 participants. Exclusion criteria would be inability to tolerate or comply with modified Atkins diet, inability to do repeat blood and urine testing, and inability to travel to Baltimore for 2 study visits 3 months apart. Participants will begin whenever they have their initial visit and conclude 12 weeks later. See Figure 1.

# Figure 1: Study Flow

Table 1: Neurocognitive and Neurobehavioral Testing			
Protocol (Repeated Day 1 and Week 12)	Purpose of Test	Area of Cognition or Behavior Evaluated	Neurocognitive Subtest Current Battery
Cognitive Assessment Protocol	Outcome Measure Development	Visuospatial reasoning	Benton Judgement of Line Orientation
		Visuospatial perception, construction, and memory	Brief Visuospatial Memory Test, NIH Toolbox Picture Story Memory
		Language	Wechsler verbal portion of IQ testing
		Visual motor integration	Beery Developmental Test of Visual Motor Integration
			Beery Developmental Test of Visual
		Visual perception	Perception
		Executive function – inhibition, attention, and switching	NIH Toolbox Flanker Inhibition and Card Sorting
		Visuospatial perception and construction	Wechsler Intelligence Scale for Children -V Block Design
Neurobehavioral			
Questionnaires	Characterize Cognitive		Caregiver Rating Scales: SCARED and
	Phenotype and Brain-		Child Behavior Checklist (CBCL) or Adult
	Behavior Relationship		Behavior Checklist (ABCL) and NIH
		Anxiety and Behavioral Phenotype	Toolbox Emotion Measures
Verbal Hippocampal	Brain-Behavior		
Measure	Relationship	Verbal memory	Hopkins Verbal Learning Test

The study flow is outlined in Figure 1. These consented adult participants will participate in an initial study visit. These participants will undergo cognitive and neurobehavioral testing and also will have baseline labs drawn and will meet with a study team member trained in modified Atkins diet for education. The labs are standard of care for diet initiation to rule out contraindications (CBC, CMP, lipids, UA, urine amino acids, free and total carnitine, Vitamin D, selenium). Blood will also be taken for genome-wide DNA methylation analysis to look for the known abnormal signature in Kabuki syndrome and see if it changes over time with the diet. Participants and/or their caregivers will keep a daily diet log and/or will be asked to download the free Carb Manager application onto their smartphone. They will send the logs and data back weekly. The application is optional, only if participants prefer it to keeping their own logs. Participants will be given urine ketone strips and asked to use and record in their diet log twice weekly. Participants will have blood ordered and drawn remotely every 3 weeks and sent securely to the study team. Beta-hydroxybutyrate will be measured on this sample as well as genome-wide DNA methylation measured every 3 weeks to see if it changes over the course of the trial. At the 6 week mark participants will also securely send a urine sample for measurement of urine ketones and amino acids to investigate metabolism while on the diet. Participants will return to Baltimore at the end of 12 weeks for a one day visit to repeat the cognitive assessment protocol, neurobehavioral measures, and repeat the initial lab tests including genome-wide DNA methylation (Figure 1).

- b. The study will last for 12 weeks for each participant. There will be 2 on site study visits. Participants will then return home for the 12 week diet. They then will return to Baltimore for a 1 day study visit.
- c. This study is not blinded for participants or investigators because that would be too difficult logistically since the participants have to keep the diet. Additionally, because this is just a very small pilot study, blinding is not necessary.
- d. Participants will receive all standard of care and treatments. None will be stopped.
- e. No placebo group will be used because this is only a pilot study and placebo groups will come in later studies.
- f. If participants cannot tolerate and/or adhere to the diet during the 12 weeks by their own self report and diet logs, they will be removed from the study.
- g. Participants can go back to their typical diet after the study ends or if they end the study early.
- h. Participants will have blood drawn 5 times and urine collected 2 times. Blood and urine collection at the initial and final study visits will be done at KKI. Most of the blood and urine will be sent to JHH core lab and are standard of care for diet

initiation and monitoring to rule out contraindications or severe side effects (CBC, CMP, lipids, UA, urine amino acids, free and total carnitine, Vitamin D, selenium). Another 2 purple top tubes of blood will also be taken and transported to the [name] lab by a study team member to run a genome-wide DNA methylation array to look for the known abnormal signature in Kabuki syndrome and see if it changes over time with the diet. The total additional blood volume taken beyond the standard of care labs for the diet will be 6 mL. In addition, participants will have blood ordered and drawn remotely every 3 weeks and sent securely to the study team. Once the study team receives it, one vial will go to JHH core lab and one to the [name] lab. Beta-hydroxybutyrate will be measured on this sample by JHH core lab every 3 weeks and the other tube will again be taken to the [name] lab to perform genome-wide DNA methylation arrays at 6 weeks to see if it changes over the course of the trial.

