### 7. Study Statistics

- a. Primary outcome variable: Change in cognitive testing protocol before and after 12 weeks of the diet
- b. Secondary outcome variables: 1) Change in anxiety measure scores after 12 weeks on the diet. 2) Change in genome-wide DNA methylation array signature while on the diet.
- c. Statistical plan including sample size justification: We will recruit 15 participants to this study with a goal of having 10 participants who complete the whole 12 weeks. We will only analyze data from participants who complete the whole 12 weeks. This number is completely generated based on the rarity of the disease model and therefore how many participants were felt were feasible to recruit. This is a very early stage, non-masked trial with no control group so no power analysis was done. To analyze the data, we will do intra-subject comparisons of the testing measures before and after 12 weeks of the diet, controlling for practice effects and for the fact the cognitive assessment protocol will be repeated 3 times in these participants. We will perform regression analysis to determine if the change is dependent on BHB levels. We will investigate whether scores on a measure of anxiety and if genome-wide DNA methylation analyses change after 12 weeks of diet and also if these potential changes moderate any change seen on cognitive assessment protocol.
- d. Participants will only stop early based on inability to tolerate the diet. With only 15 participants, there will be no interim data analysis to stop early.

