- d. Any physical data forms will be kept in a locked office in a locked cabinet to which only the PI has the key. The linking document with patient identifiers and study ID numbers will be kept on a password protected computer in the locked office, within a password protected file. This file will be kept separate from all data files including imaging data and testing results. These files will be deidentified and marked with a study identifier only and stored on a secure server JHH OneDrive. Data collected through the CarbManager app, for those who choose to use it, will not have any identifiable information in it and will be emailed securely to the study team.
- e. Participants may incur a financial toll by having to travel to Baltimore. We will minimize this by making the needed travel clear in screening.

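### Neither reason given for not blinding (diet logistics, small pilot size) applies to scoring completed test sheets, and the plan does not hide the visit from the scorer

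*Combined protocol and SAP*

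**What the plan says.** Section 4 (Study Procedures), item c gives two reasons for an open study. The first is practical: "This study is not blinded for participants or investigators because that would be too difficult logistically since the participants have to keep the diet". The second is introduced as an additional reason: "because this is just a very small pilot study, blinding is not necessary". Item e of the same section rules out a concurrent comparator at this stage: "No placebo group will be used because this is only a pilot study and placebo groups will come in later studies".

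Section 7 (Study Statistics), item a defines the primary outcome as "Change in cognitive testing protocol before and after 12 weeks of the diet". No single test or composite is named. Item c of that section says "we will do intra-subject comparisons of the testing measures before and after 12 weeks of the diet", with control for practice effects and for repeated administration. It also describes the design openly: "This is a very early stage, non-masked trial with no control group so no power analysis was done".

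Table 1 in Section 4 lists the battery by domain and test name. Visuospatial perception, construction and memory are covered by "Brief Visuospatial Memory Test, NIH Toolbox Picture Story Memory", and visual motor integration by the Beery test. Neither the table nor the text says who administers or scores any test, how it is scored, or whether the scorer knows the visit. Section 8, item d says of data files that "These files will be deidentified and marked with a study identifier only". That concerns confidentiality, not masking of the visit.

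**The concern.** Both reasons in item c concern something other than scoring. Participants must know they are on the diet, but a finished response sheet can be scored later without its visit label. Small size is not a reason either: if a scorer expects improvement and leans that way on judgement items at Week 12, the mean change moves by the same amount whether 10 or 100 people are tested.

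The design gives no protection against such a shift. There is no control arm in which it could cancel, and the adjustments named in Section 7, item c (practice and repetition) do not address it. The tests most likely to involve scorer judgement also lie close to the visuospatial hypothesis set out in Section 3. Section 3 says the pilot could lead to a larger trial, so an artefact read as a signal would have consequences.

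**Working it through.** **The plan's own figure.** Section 4, item a expects about 30% dropout and wants data from 10 participants. 10 / (1 − 0.30) = 14.3, rounded up to 15, which matches the stated 15. The documents give no alpha, power, effect size or SD of change, so there is no other figure to reproduce.

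**Inputs from the documents.** 10 completers; primary outcome a within-person change; no control group. I count nine tests under the cognitive assessment protocol in Table 1: line orientation, Brief Visuospatial Memory Test, Picture Story Memory, Wechsler verbal, Beery Visual Motor Integration, Beery Visual Perception, Flanker, Card Sorting and Block Design.

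**Inputs assumed.** Paired t-test at two-sided 5%; true change of zero; Week 12 scoring shift b = 0.1, 0.2 or 0.3 SD of the raw score on an affected test; retest correlation r = 0.7 or 0.8; two affected tests (Brief Visuospatial Memory Test and Beery Visual Motor Integration); correlation between change scores ρ = 0.3 or 0.5.

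**One affected test analysed alone.**
- SD of change = √(2(1 − r)): 0.632 at r = 0.8 and 0.775 at r = 0.7.
- Standardised shift d = b / SD of change. Non-centrality = d√10, with 9 degrees of freedom.
- Example: b = 0.2 and r = 0.8 give d = 0.2 / 0.632 = 0.316 and non-centrality 1.00.

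| Shift b (raw SD) | False-positive rate, r = 0.8 | False-positive rate, r = 0.7 |
|---|---|---|
| 0.1 | 7.3% | 6.6% |
| 0.2 | 14.6% | 11.3% |
| 0.3 | 26.9% | 19.5% |

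**Mean of nine tests, two affected.**
- SD of the mean change, in units of one test's SD of change = √((1 + 8ρ)/9): 0.615 at ρ = 0.3 and 0.745 at ρ = 0.5.
- Standardised shift of the mean = d × (2/9) / that SD.
- Largest case (b = 0.3, r = 0.8, ρ = 0.3): 0.474 × 0.222 / 0.615 = 0.171, giving 7.8%.
- Smallest case (b = 0.1, r = 0.7, ρ = 0.5): 0.129 × 0.222 / 0.745 = 0.039, giving 5.1%.

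**Unit of the shift.** If the shift is stated in SDs of the change score instead, a single test gives 5.9%, 8.8% and 13.6% at 0.1, 0.2 and 0.3. The lower figures reflect a smaller shift on the raw scale.

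**Role of n.** The bias in the estimate does not depend on n. The false-positive rate it causes rises with n: at 0.3 SD of change it is 13.6% with 10 participants and 19.2% with 15. A small sample therefore makes the shift harder to detect but does not remove it from the estimate.

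**The case against.** The strongest reply is that the limitation is disclosed. The protocol calls the study early-stage, non-masked and uncontrolled, and defers placebo groups to later work. In an exploratory pilot of about 10 completers, masked scoring is a refinement and corrects no contradiction or wrong number. That stands, and it limits the weight of the point.

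Several stronger readings are tempting, and the documents do not support them:
- A reader might infer that drawing tests are scored by hand by someone who knows the visit. The documents never describe scoring. With investigators unblinded and no masking planned this is likely, but it remains an inference. Which tests rest on scorer judgement is also an assumption.
- A reader might take small size as the protocol's only reason. Logistics comes first in item c.
- A reader might conclude that the bias passes in full into the primary outcome. About two of nine tests are in question, and their weight is unknown because no composite is defined.
- A reader might suppose that masked scoring is known to need no extra staff. Staffing is not described. Existing staff can work from coded sheets without a second reader, but someone who ran both visits may recognise some of them.

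Masked scoring is also only a partial remedy. It leaves participant effort, examiner behaviour and practice effects untouched. Section 7, item c mentions three administrations of the protocol, whereas this study has two testing visits, so an earlier administration may already have been scored.

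**Conclusion.** The point holds as a low-cost improvement of minor severity. The conclusion in item c that blinding is not necessary does not follow for scoring, and the plan has no step that hides the visit from whoever scores judgement-based tests. With no control arm, a scorer's shift at Week 12 could not be told apart from a diet effect.

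The size is unknown. Under the assumptions above, the nominal 5% becomes 7% to 27% if one affected test is analysed alone, which the reference in Section 7, item c to testing measures allows. It becomes 5.1% to 7.8% if the primary is a nine-test mean with two affected. These figures illustrate a risk. They are not evidence that scoring in this study is biased, and the upper figure should not be read as the error rate of the primary outcome.

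**What to change.** Replace the sentence in Section 4, item c that calls blinding unnecessary. The new text should say:
- Treatment and test administration are open-label.
- Response sheets for tests that need scorer judgement (on present assumptions the Brief Visuospatial Memory Test and Beery Visual Motor Integration; the investigator should confirm the list) carry a code without visit or date.
- Existing study staff score these sheets in one batch, in random order, after both visits are complete, where possible by a team member who did not run the visit.
- Any earlier administration used in the comparison is coded and scored the same way if its sheets have been kept.

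Section 7, item c should state who scores and that these tests are scored with the visit hidden.

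The cost is relabelling at most 15 × 2 = 30 sets of sheets, plus any retained from an earlier administration, and scoring them at the end. Recruitment, visits and participant burden do not change. The downsides are that scores come later, that a scorer may still recognise some sheets, and that expectancy of participants and examiners and practice effects remain.

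### In the visible text, CMP and lipids are scheduled only before the diet and at week 12; adding them to the planned week-6 draw is a cheap, low-severity safety improvement

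*Combined protocol and SAP*

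**What the plan says.** The study-flow text of section 4 lists the panel at the initial visit: CBC, CMP, lipids, UA, urine amino acids, carnitine, vitamin D and selenium. At the end of 12 weeks participants return and "repeat the initial lab tests including genome-wide DNA methylation". Item h says that most of this blood and urine is standard of care for diet "initiation and monitoring to rule out contraindications or severe side effects".

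Between the two visits blood is drawn remotely every 3 weeks. Item h says: "Once the study team receives it, one vial will go to JHH core lab". The planned test on that vial is beta-hydroxybutyrate (BHB): "Beta-hydroxybutyrate will be measured on this sample by JHH core lab every 3 weeks". The other tube is for DNA methylation. The study-flow text also plans "At the 6 week mark participants will also securely send a urine sample for measurement of urine ketones and amino acids", and for home testing, "Participants will be given urine ketone strips and asked to use and record in their diet log twice weekly".

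Section 8, item a, names kidney stones, acidosis and hyperlipidemia among the diet's risks. Items b and c of that section provide baseline labs and an exam, weekly check-ins, a role responsible for reporting and responding to adverse events, and a DSMB.

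On stopping, section 4, item f, says that participants who cannot tolerate or adhere to the diet, "by their own self report and diet logs, they will be removed from the study". Section 7, item d, says: "Participants will only stop early based on inability to tolerate the diet".

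**The concern.** A panel that is meant partly for monitoring can change what happens to a participant only if a result arrives while the diet can still be altered. On the visible schedule, the only repeat comes when the study diet finishes. It can document a side effect, but it cannot guide the 12 weeks of diet that the study asks for.

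The interim measures serve other purposes. BHB and ketone strips show the degree of ketosis. They do not measure bicarbonate, creatinine or lipids. Weekly check-ins pick up what participants or caregivers notice and report. The gap is therefore confined to changes without symptoms, some of which fall under risks that the protocol itself names.

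The stopping wording adds to this. Read literally, section 7, item d, gives intolerance as the sole ground for stopping early, so an abnormal result in a participant who feels well is not a listed reason.

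What is at stake is the safety of at most 15 adults over 12 weeks. The cognitive outcome and its analysis do not depend on it.

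**Working it through.** **Inputs.** Diet period 12 weeks (section 4, item b). Blood drawn 5 times and urine collected 2 times (section 4, item h). Remote blood every 3 weeks (study-flow text and item h). 15 recruited, about 30% dropout, target of 10 completers (section 4, item a; section 7, item c).

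**1. Reproduce the plan's draw count.** Initial visit + weeks 3, 6 and 9 + final visit = 5, which matches item h.

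**2. Place the panel on the draws.**

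| Draw | Planned blood tests | CMP and lipids? |
|---|---|---|
| Initial visit | panel, methylation | yes |
| Week 3 | BHB; methylation per the study-flow text | no |
| Week 6 | BHB, methylation | no |
| Week 9 | BHB; methylation per the study-flow text | no |
| Week 12 | panel, methylation | yes |

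The panel is on 2 of 5 draws and on 0 of 3 interim draws. The study-flow text has methylation every 3 weeks, whereas item h has the interim array at 6 weeks. Either reading leaves the last column unchanged.

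**3. Length of the gap.** 12 × 7 = 84 days, the whole diet period. With one panel added at week 6, the longest gap is 6 × 7 = 42 days, and 84 − 42 = 42 days of diet remain (42/84 = 50%), less shipping and assay time, which the protocol does not give. One added panel at week 3 or week 9 would leave a longest gap of 9 × 7 = 63 days, so week 6 is the best single choice on this measure.

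**4. Number of extra panels.** Assume all 15 start the diet. Dropouts: 15 × 0.30 = 4.5, so 4 to 5. If all leave before week 6, 15 − 5 = 10 or 15 − 4 = 11 reach it; if all leave after, 15 do. That gives 10 to 15 extra panels.

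**5. Effect on completers.** 15 − 5 = 10 to 15 − 4 = 11 completers are expected. One stop for a laboratory finding leaves 10 − 1 = 9 to 11 − 1 = 10, against the target of 10.

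**6. The week-6 urine.** Item h counts 2 urine collections. The initial and final visits already use both, and the study-flow text adds one at week 6, making 3. The week-6 urine therefore cannot be treated as settled, and a UA at that time depends on it.

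The documents give no rate of silent laboratory abnormality on this diet, so no expected number of cases is calculated.

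**The case against.** The strongest reply is that nothing has been breached. A panel before and after a 12-week diet fits the description of standard-of-care monitoring, and no statement in the documents makes 12 weeks too long an interval for screened adults. That stands. A reader might infer that the protocol contradicts its own monitoring purpose or falls below a standard; the documents do not support either.

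A reader might also infer that participants go unmonitored between visits. That is wrong too. There are weekly check-ins, twice-weekly ketone strips, BHB every 3 weeks, diet clinicians for consultation (section 6) and a DSMB. Standard of care continues (section 4, item d), so clinically indicated tests are not barred. BHB tracks ketone load, which bears indirectly on acidosis. What remains is narrower: none of these is a scheduled test of acid-base status, renal function or lipids.

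On stopping, it can be argued that intolerance covers medical intolerance, and that the role responding to adverse events could withdraw a participant. It would go too far to say that the protocol forbids acting on a laboratory result. The wording is nonetheless restrictive enough to deserve a clarifying clause.

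Two practical objections also stand. Mailed blood may not suit every CMP analyte, and the status of the week-6 urine is unclear. Both limit the fix, and it is shaped accordingly. Finally, Figure 1 may show an interim panel. If it does, the scheduling point falls away.

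**Conclusion.** The point holds as a low-severity suggestion. In the visible text, CMP and lipids are scheduled on none of the 3 interim draws, so the first planned test able to show a silent acid-base, renal or lipid change comes as the 84-day study diet ends. One week-6 panel halves that interval to 42 days. Participants may choose to stay on the diet after the study (section 4, item g), so the week-12 result is not useless, but it comes too late to guide the study diet.

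The conclusion rests on three conditions: Figure 1 contains no interim panel; remote draws fall at weeks 3, 6 and 9, as the count of 5 implies; and all 15 participants start the diet, which matters only for the 10-to-15 range. How many participants would benefit cannot be estimated from the documents. Sample size and the primary analysis plan do not change.

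**What to change.** Check Figure 1 first. If it shows no interim panel:

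1. **Section 4, item h.** Add CMP and lipids to the planned week-6 remote draw. Where an analyte such as bicarbonate may not survive shipping, have the drawing laboratory run it.
2. **Section 8, item c.** State that the role already responsible for adverse events reviews these results on arrival and refers concerns to the DSMB. Leave action levels to the sponsor and the DSMB.
3. **Section 7, item d.** Replace the present sentence with, for example: *A participant may stop early because of intolerance of the diet or because of a clinically significant laboratory abnormality.*
4. **UA at week 6: optional.** First confirm whether the week-6 urine is planned and correct the count in item h. If the sample is confirmed and mailed urine is valid for the test, add UA; otherwise omit it.

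**Cost.** 10 to 15 extra panels, with no new visit or draw date. One vial of each remote draw already goes to the core laboratory, and section 11 puts laboratory costs on the grant. Unit prices are not given. The downsides are possibly one more tube at week 6, arrangements for local assay, some repeat tests for mild abnormalities, and the possible loss of a completer, which would leave 9 to 10 against the target of 10.
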